#### **9.10.4 Vital Status**

To ensure current and complete vital status for survival data is available at the time of database locks, updated vital status for survival data may be requested during the study by the Sponsor. For example, updated vital status for survival data may be requested before but not limited to, an eDMC review, interim and/or final analysis. Upon Sponsor notification, all participants who do not/will not have a scheduled study visit or study contact during the Sponsor-defined time period will be contacted for their vital status for survival data (excluding participants that have a previously recorded death event in the collection tool).

#### **9.10.5 Study Design/Dosing/Procedures Modifications Permitted within Protocol Parameters**

It is understood that the current study may employ some or none of the alterations described above. Any alteration made to this protocol to meet the study objectives must be detailed by the Sponsor in a letter to the Trial File and forwarded to the investigator for retention. The letter may be forwarded to the IRB/IEC at the discretion of the investigator.

#### **9.11 Medical Resource Utilization and Health Economics**

Medical resource utilization and health economics data, associated with medical encounters, will be collected in the CRF by the investigator and study-site personnel for all participants throughout the study. Protocol-mandated procedures, tests, and encounters are excluded.

The data collected may be used to conduct exploratory economic analyses and will include:

- All-cause hospitalizations and emergency room visits, from the time of treatment allocation through 90 days following cessation of study treatment, or 30 days following cessation of study treatment, if the participant initiates new anticancer therapy, whichever is earlier.

## 10 Statistical Analysis Plan

### 10.1 Statistical Analysis Plan Summary

This section outlines the statistical analysis strategy and procedures for the study. Changes in analyses made after the protocol has been finalized, but prior to final database lock, will be documented in a supplemental statistical analysis plan (sSAP) and referenced in the clinical study report (CSR) for the study. Post-hoc exploratory analyses will be clearly identified in the CSR. The study will use an adaptive approach, with on-treatment data guiding study adaptation and success or futility of each combination in each study subpopulation.

Currently, 30 participants are being treated with MK-4280 200 mg Q3W, including 10, 7, 8, and 5 participants in Biomarker Group I, II, III, and IV, respectively. These 30 participants treated with MK-4280 200 mg Q3W may be replaced with 30 additional participants treated with MK-4280 at 800 mg Q3W after the approval of Amendment 05. Consequently, the total treated sample size is changed from 288 to 318. The replacement number may depend on results of interim analyses, including estimated posterior probabilities of meeting the target response rate at the 800 mg dose. All key statistical elements in this section including, but not limited to, statistical efficacy, futility, sample size and power are based on participants receiving pembrolizumab at a dose of 200 mg Q3W in combination with 25 mg MK-1308 Q6W, 800 mg Q3W MK-4280 and lenvatinib daily. The combination with MK-4280 in this section is specifically referring to the participants treated with the combination pembrolizumab with 800 mg MK-4280 Q3W from C1D1 unless more details are provided.

Key elements of the SAP are summarized below; comprehensive details are provided in Sections 10.2 through 10.12.

Study Design Overview	This is an unblinded, open-label adaptively randomized Phase 2 study of a biomarker-directed, pembrolizumab-based (MK-3475-based) combination therapy in study participants with advanced NSCLC.
Treatment Assignment	All participants will be selected by a clinical classifier based on GEP and TMB. Participants will be assigned to 1 of 4 biomarker-defined groups and will be randomized to receive pembrolizumab at a dose of 200 mg IV Q3W in combination with MK-1308 (anti-CTLA-4), MK-4280 (anti-LAG-3), or lenvatinib. Randomization to treatment will be done using a prespecified adaptive randomization algorithm in an unblinded fashion. Furthermore, due to the different start time of 3 pembrolizumab-based combination treatments, an unequal randomization ratio may be used first and then randomization schedules will be adjusted to equalize treatment arm enrollment per biomarker-defined group depending on the time of introducing the delayed combination treatments in order to meet study analysis milestones.
Analysis Populations	Efficacy and Safety: All Subjects as Treated (ASaT)
Primary Endpoint(s)	1. ORR based on RECIST 1.1 as assessed by local site review
Key Secondary Endpoints	1. PFS based on RECIST 1.1 as assessed by local site review 2. OS 3. Safety as assessed by the number of participants experiencing AEs and the number of participants discontinuing study drug due to AEs.

Statistical Methods for Key Efficacy/Immunogenicity/ Pharmacokinetic Analyses	In each of the 4 biomarker-defined groups, the primary hypothesis that the ORR is greater than CCI within the GEP low TMB low group, CCI within the GEP low TMB hi , GEP hi TMB low groups, and CCI within the GEP hi TMB hi group will be evaluated using a Bayesian posterior probability. For the primary hypothesis, the ORR in each pembrolizumab-combination therapy group will be considered significantly larger than that expected from historical pembrolizumab monotherapy (CCI in the GEP low TMB low , GEP low TMB hi , GEP hi TMB low , and GEP hi TMB hi groups, respectively) if there is at least 95% posterior probability that the true ORR is greater than CCI for the GEP low TMB low , GEP low TMB hi , GEP hi TMB low , and GEP hi TMB hi groups, respectively.
Statistical Methods for Key Safety Analyses	Safety will be evaluated using descriptive statistics.
Interim Analyses	
The study incorporates an adaptive randomization design, in which multiple interim analyses may be performed. The primary endpoint of ORR will be used for all interim analyses.
 
The first interim analysis for each combination therapy will occur after at least 10 participants have at least 12 weeks of follow-up. Participants' response data will be closely monitored throughout the study and subsequent interim analyses may be performed with a minimum of 2 additional participants in each combination therapy achieving 12 weeks of follow-up.
 
At each interim analysis, either combination therapy arm in any biomarker-defined group may be terminated due to either futility, safety, or if the maximum number of participants for the combination therapy has been reached. Any biomarker-defined group may be terminated due to futility or safety of all three combination therapies or the maximum number of participants for each biomarker-defined group has been reached.

Multiplicity	This is an adaptive randomization study. No multiplicity adjustment will be employed. Estimates of the false positive rate (probability of incorrectly selecting any futile combination therapy) were derived via simulation studies, and details are provided in Section 10.8.
Sample Size and Power	
The estimated historical control ORRs for study participants on pembrolizumab monotherapy treatment are CCI in GEPlowTMBlow, GEPlowTMBhi, GEPhiTMBlow, and GEPhiTMBhi, respectively. The decision rules for futility and efficacy were derived using these underlying assumptions.
 
Table 12 shows the operating characteristics of this design with maximum sample size of approximately 66 for the GEPlowTMBlow, GEPlowTMBhi, and GEPhiTMBlow groups, and maximum sample size of approximately 90 for GEPhiTMBhi group. The probability of correctly selecting the combination therapy when the true ORR for that combination therapy is increased approximately 25 to 30 percentage points over estimated historical control ORR is approximately CCI in the GEPlowTMBlow, GEPlowTMBhi, GEPhiTMBlow, and GEPhiTMBhi groups, respectively. The probability of correctly selecting all combination therapies when the true ORR for all combination therapies is increased approximately 25 to 30 percentage points over the estimated historical control ORR is approximately CCI in the GEPlowTMBlow, GEPlowTMBhi, GEPhiTMBlow, and GEPhiTMBhi groups, respectively. The average sample size for each combination therapy under various assumptions is also provided in Table 12.

## **10.2 Responsibility for Analyses/In-House Blinding**

The interim and final statistical analysis of the data obtained from this study will be conducted by, or under the direct auspices of, the Early Clinical Development Statistics Department of the Sponsor.

This study is being conducted as an open-label study, ie, study participants, investigators, and Sponsor personnel will be aware of participant treatment assignments after each participant is enrolled and treatment is assigned.

## **10.3 Hypotheses/Estimation**

Objectives and hypotheses of the study are stated in Section 4 – Objectives/Hypotheses & Endpoints.

## **10.4 Analysis Endpoints**

Efficacy and safety endpoints that will be evaluated are listed below, followed by descriptions of the derivations of selected endpoints.

### **10.4.1 Efficacy Endpoints**

The primary efficacy endpoint is objective response rate. Study participants will be defined as having an objective response if they have the best response as CR or PR based on RECIST 1.1 at any time during the study prior to initiation of follow-up therapy. The objective response for the primary analysis will be determined by local site radiologic review, with confirmatory assessment as required per RECIST 1.1. Participants with unknown or missing response information will be treated as nonresponders.

Secondary efficacy endpoints include the following:

- (1) Progression-free survival, defined as the time from allocation to the first documented disease progression according to RECIST 1.1, as assessed by local site radiologic review, or death due to any cause, whichever occurs first.
- (2) Overall survival, defined as the time from the date of allocation to the date of death due to any cause.

### **10.4.2 Safety Endpoints**

A description of safety measures is included in Section 9.3 and Section 9.5. The analysis strategy for safety parameters is summarized in Section 10.6.2.

## **10.5 Analysis Populations**

### **10.5.1 Efficacy Analysis Population**

The ASaT population will be used for the analysis of efficacy in this study. The ASaT population consists of all allocated study participants who have received study treatment.

## **10.5.2 Safety Analysis Population**

The ASaT population will also be used for the analysis of safety data in this study. At least 1 laboratory or vital sign measurement obtained subsequent to at least 1 dose of study treatment is required for inclusion in the analysis of each specific parameter. To assess change from baseline, a baseline measurement is also required.

## **10.6 Statistical Methods**

### **10.6.1 Statistical Methods for Efficacy Analysis**

#### **10.6.1.1 Objective Response Rate (ORR)**

In each of the 4 biomarker-defined groups, the primary hypothesis that the ORR is greater than CCI within the  $GEP^{low}TMB^{low}$ ,  $GEP^{low}TMB^{hi}$ ,  $GEP^{hi}TMB^{low}$ , and  $GEP^{hi}TMB^{hi}$  groups, respectively, will be evaluated using a Bayesian posterior probability. The ORR in each of the pembrolizumab-combination therapies will be considered larger than CCI within the  $GEP^{low}TMB^{low}$ ,  $GEP^{low}TMB^{hi}$ ,  $GEP^{hi}TMB^{low}$ , and  $GEP^{hi}TMB^{hi}$  groups, respectively, if there is at least 95% posterior probability supporting the hypothesis. A Beta (CCI), Beta (CCI), Beta (CCI), and Beta (CCI) prior distribution will be used for the  $GEP^{low}TMB^{low}$ ,  $GEP^{low}TMB^{hi}$ ,  $GEP^{hi}TMB^{low}$ , and  $GEP^{hi}TMB^{hi}$  groups, respectively. For the primary hypothesis, study participants without disease assessment after the start of treatment will be considered as nonresponders in ORR estimation. When computing the ORR at the interim analyses, only study participants with adequate follow-up (at least 12 weeks) will be included in the denominator. Participants with confirmed or unconfirmed response, if confirmation is not available at the time of the interim analyses, will be included in the numerator. At the final analysis, all enrolled participants who received at least one dose of study drug will be included in the denominator and only participants with confirmed response will be included in the numerator. A confirmed response will be counted as a response regardless of relapse at a later point during the course of the study. The posterior distribution of ORR for all combination therapies will also be provided at the final analysis, as well as the CCI percentile and the CCI percentile of the distribution. The frequentists' CCI confidence interval (CI) will also be estimated and reported.

#### **10.6.1.2 Progression-Free Survival (PFS)**

The Kaplan-Meier method will be used to estimate the PFS curve. The median PFS and its associated CCI confidence interval (CI) will be estimated and reported. The Kaplan-Meier estimates of the PFS rate at 6 months and other time points of interest will also be reported. Because disease progression is assessed periodically, PD can occur any time in the time interval between the last assessment where PD was not documented and the assessment when PD is documented. For this analysis, for study participants who have PD, the true date of disease progression will be approximated by the date of first assessment at which PD is objectively documented using RECIST 1.1, regardless of discontinuation of study drug. Death is always considered as a confirmed PD event. Participants without documented PD/death will be censored at the last disease assessment date. In the event that participants without documented PD/death have new anticancer treatment initiated, the

participants will be considered censored at last disease assessment before new anticancer treatment.

### 10.6.1.3 Overall Survival (OS)

The Kaplan-Meier method will be used to estimate the OS curve. The median OS and its associated **CCI** CI will be estimated and reported. The Kaplan-Meier estimates of the OS rate at 6 months and other time points of interest will also be reported. A sensitivity analysis of OS that censors study participants at the time of initiation of new anticancer treatment will also be performed. Table 11 summarizes the efficacy analyses.

Table 11 Analysis Strategy for Efficacy Variables

Endpoint/Variable (Description, Time Point)	Primary vs. Supportive Approach a	Statistical Method	Analysis Population	Missing Data Approach
Primary Hypothesis #1				
Overall response rate (ORR) by RECIST 1.1 as assessed by local site	P	Bayesian Approach	ASaT	Study participants with missing data are considered nonresponders
Secondary Endpoints				
Secondary Objectives				
Progression-free-survival (PFS) by RECIST 1.1 as assessed by local site	P	Kaplan-Meier method for PFS curve estimation and summary statistics with CCI will be reported.	ASaT	Censored at last assessment (before new anticancer treatment)
Overall survival (OS)	P	Kaplan-Meier method for OS curve estimation and summary statistics with CCI will be reported.	ASaT	Censored at last date
Overall survival (OS)	S	Kaplan-Meier method for OS curve estimation and summary statistics with CCI will be reported.	ASaT	Censored at last assessment (before new anticancer treatment)
a P=Primary approach; S=Supportive approach.				

### 10.6.2 Statistical Methods for Safety Analysis

Safety and tolerability will be assessed by clinical review of all relevant parameters including AEs, SAEs, laboratory tests, vital signs, ECG measurements, and physical examinations.

Adverse events will be summarized by counts and frequencies. Laboratory tests, vital signs, and other safety endpoints will be summarized as appropriate.

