
 
Objective: To determine the safety and tolerability of pembrolizumab in combination with MK-1308, MK-4280, or lenvatinib. Safety and tolerability to different specific pembrolizumab-based combinations will be assessed independently in each biomarker-defined group.
 
	
 
Number of Participants Experiencing Adverse Events (AEs).
 
Number of Participants Discontinuing Study Drug Due to AEs.
 

Tertiary/Exploratory	

Biomarkers for different specific pembrolizumab-based combinations will be assessed independently in each biomarker-defined group.
 
 
Objective: To evaluate the clinical activity (as assessed by ORR and PFS) using modified RECIST 1.1 for immune-based therapeutics (iRECIST) [Seymour, L., et al 2017], as assessed by local site review.
 
Objective: To evaluate clinical responses based upon individual biomarkers (PD-L1 immunohistochemistry [IHC] GEP and TMB).
 
Objective: To explore additional classifiers of primary resistance to PD-1 blockade beyond GEP and TMB based on additional immune evaluation of baseline tissue.
 
Objective: To assess the concordance in neoantigen mutation load as measured by TMB gene panel vs whole exome sequencing/RNA-seq
 
	
 
Clinical activity (as assessed by ORR and PFS) of specific pembrolizumab-based combinations using modified RECIST 1.1 for immune-based therapeutics (iRECIST), as assessed by local site review.
 

Objective/Hypothesis	Endpoint

 
Objective: To identify molecular (genomic, metabolic, and/or proteomic) biomarkers that may be indicative of clinical response/resistance, safety, pharmacodynamic activity, and/or the mechanism of action of pembrolizumab based combinations.
 
Objective: To collect and build on the pharmacokinetic (PK) and anti-drug antibody (ADA) experiences of MK-1308 and MK-4280 in combination with pembrolizumab.
 
	
 
Germline genetic variation, genetic (DNA) mutations from tumor, tumor and blood RNA variation, proteomics and IHC, and other blood-derived biomarkers.
 
PK profiles and ADA rates of MK-1308 and MK-4280 in combination with pembrolizumab
 

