### **5.5.3 Rationale for Dose Intervals and Study Design**

As explained in Section 5.5.1, Rationale for Pembrolizumab Fixed-Dose (Standard of Care and Combination-Based Therapy), pembrolizumab will be administered at a dose of 200 mg IV Q3W. The doses and dosing intervals of the combination agents are explained in Section 5.5.2, Rationale for Combination Agent Dose Selection. Study participants will be

treated with a maximum of 35 treatments (approximately 2 years) of pembrolizumab. Combination treatment with MK-1308 or MK-4280 also will be given for a maximum duration and discontinued upon completion of the 35th cycle of pembrolizumab. For the lenvatinib combination arm, if a participant completes 35 infusions of pembrolizumab, they may continue with lenvatinib alone until disease progression or toxicity.

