### **9.3.1 Time Period and Frequency for Collecting AE, SAE and Other Reportable Safety Event Information**

All AEs, SAEs and other reportable safety events that occur after the consent form is signed but before treatment allocation/randomization must be reported by the investigator if the participant is receiving placebo run-in or other run-in treatment, if the event cause the participant to be excluded from the trial, or is the result of a protocol-specified intervention, including but not limited to washout or discontinuation of usual therapy, diet, or a procedure.

- All AEs from the time of treatment allocation/randomization through 30 days following cessation of study treatment must be reported by the investigator.
- All AEs meeting serious criteria, from the time of treatment allocation/randomization through 90 days following cessation of study treatment, or 30 days following cessation of study treatment if the participant initiates new anticancer therapy, whichever is earlier must be reported by the investigator. For participants treated with lenvatinib, all AEs meeting serious criteria, from the time of treatment allocation/randomization through 120 days following cessation of study treatment, or 30 days following cessation of study treatment if the participant initiates new anticancer therapy, whichever is earlier must be reported by the investigator.
- All pregnancies and exposure during breastfeeding, from the time of treatment allocation/randomization through 120 days following cessation of study treatment, or 30 days following cessation of study treatment if the participant initiates new anticancer therapy must be reported by the investigator.
- Additionally, any SAE brought to the attention of an investigator at any time outside of the time period specified above must be reported immediately to the Sponsor if the event is considered to be drug-related.

Investigators are not obligated to actively seek AE or SAE or other reportable safety events in former study participants. However, if the investigator learns of any SAE, including a death, at any time after a participant has been discharged from the study, and he/she considers the event to be reasonably related to the study treatment or study participation, the investigator must promptly notify the sponsor.

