Other Screening Tests	
 
• Follicle-stimulating hormone and estradiol (as needed in women of non-childbearing potential only) 
 
• <math>\beta</math> human chorionic gonadotropin (<math>\beta</math> hCG) pregnancy test (as needed for women of childbearing potential) within 24 hours of first dose
 
 
 
 
Thyroid panel: TSH, FT4, FT3/T3Serology

ACTH=adrenocorticotrophic hormone; MCH=mean corpuscular hemoglobin; MCV=mean corpuscular volume; RBC=red blood cell; TSH=thyroid-stimulating hormone; WBC=white blood cell.
 
a. Urea is acceptable if BUN is not available as per institutional standard.
 
b. Performed only if considered the local standard of care.
 
c. Performed at screening on all participants and then only for pembrolizumab plus MK-4280 treatment arm
 
d. Performed at screening on all participants and then only for pembrolizumab plus MK-1308 treatment arm
 
e. Only required for participants receiving pembrolizumab plus lenvatinib.
	

Investigators must document their review of each laboratory safety report.

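### SAE windows, maximum treatment duration and scheduled tests differ by arm, but Section 10.6.2 plans only crude counts, so several safety counts are not like-for-like across the combinations

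*Combined protocol and SAP*

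**What the plan says.** Analysis. Section 10.1 states "Safety will be evaluated using descriptive statistics", and Section 10.6.2 adds "Adverse events will be summarized by counts and frequencies". Section 10.12 summarizes exposure in cycles, separately from the AE tables. Section 4 says "Safety and tolerability to different specific pembrolizumab-based combinations will be assessed independently in each biomarker-defined group". One named safety endpoint is the number of participants with any AE; the other is "Number of Participants Discontinuing Study Drug Due to AEs".

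Collection windows (Section 9.3.1). All AEs are collected to 30 days after treatment stops, in every arm. SAEs are collected to 90 days in the MK-1308 and MK-4280 arms. The lenvatinib rule differs: "For participants treated with lenvatinib, all AEs meeting serious criteria, from the time of treatment allocation/randomization through 120 days following cessation of study treatment". In every arm the SAE window shortens to 30 days once new anticancer therapy starts, and drug-related SAEs that come to light outside the window are still reportable.

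Treatment duration (Sections 5.5.3 and 8.1). MK-1308 and MK-4280 stop with the 35th cycle of pembrolizumab. Participants in the lenvatinib arm who complete 35 infusions have another option: "they may continue with lenvatinib alone until disease progression or toxicity".

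Monitoring. Table 3 gives the lenvatinib arm a day-8 contact in cycle 1 and mandatory day-15 visits in cycles 1 and 2. Table 13 in Appendix 2 says of amylase and lipase: "Performed at screening on all participants and then only for pembrolizumab plus MK-4280 treatment arm". Its other footnotes restrict post-screening cortisol and ACTH to the MK-1308 arm, and magnesium to the lenvatinib arm.

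**The concern.** A crude proportion with an event depends on how long and how closely participants were watched. Here both depend on the arm, and the planned summary accounts for neither. Two combinations with the same underlying event rate could show different SAE or AE-discontinuation counts, and a laboratory finding may be rarer in one arm because nobody was scheduled to test for it. One example is in the protocol itself: a footnote to Table 8 uses Grade 3 or higher amylase and lipase elevations to illustrate laboratory abnormalities during lenvatinib treatment, yet that arm has no scheduled amylase or lipase test after screening.

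The counts will be read across arms. Section 3.2 gives the goal as finding which combination works best in each biomarker subset, and Sections 7.3.1 and 10.1 allow an arm to be dropped for safety.

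**Working it through.** The documents give no AE rate, power or precision for safety, so there is no design figure to reproduce. As a check on the cap, 35 cycles x 21 days = 735 days = 2.01 years, which matches the stated two years or so. All hazards, proportions and durations below are assumptions. T is days on treatment.

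**1. Windows compared**
- All AEs after treatment: 30/30 = 1.00.
- SAEs after treatment: 120/90 = 1.33.
- Whole SAE window, (T+120)/(T+90): 1.196 at T = 63, 1.139 at T = 126, 1.088 at T = 252, 1.036 at T = 735.

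**2. SAE proportion over the whole window.** Assume the same constant hazard in both arms, and a proportion p with an SAE by T+90. By T+120 the proportion is 1 - (1-p)^[(T+120)/(T+90)]. Example with T = 126 and p = 40%: 1 - 0.6^(246/216) = 44.1%, a gap of 4.1 points with no difference in risk.

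| T (days) | Gap at p = 20% | Gap at p = 50% |
|---|---|---|
| 63 | 3.4 points | 6.4 points |
| 126 | 2.4 | 4.6 |
| 252 | 1.6 | 2.9 |
| 735 | 0.6 | 1.2 |

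**3. Effect of new anticancer therapy.** If a fraction f has the SAE window cut to 30 days in both arms, the gap is multiplied by (1-f). In the example it falls from 4.1 to 2.1 points at f = 50% and to 0.8 at f = 80%.

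**4. Post-treatment period alone.** With hazard h per year, compare 1 - exp(-h x 90/365) with 1 - exp(-h x 120/365). For h = 0.2, 0.5 and 1.0 the results are 4.8, 11.6 and 21.9% against 6.4, 15.2 and 28.0%. The unrounded gap is 1.55 points at the low end and 6.17 at the high end. A participant who already had an SAE on treatment adds nothing to a participant-level count. If 40% had one, the range becomes 0.6 x 1.55 = 0.9 to 0.6 x 6.17 = 3.7 points. If half also start new therapy within 90 days, it becomes about 0.5 to 1.8.

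**5. Lenvatinib alone after cycle 35.** An extra 90 to 365 days lengthens the all-AE window from 765 days to 855 or 1,130, a factor of 1.12 to 1.48, for those who reach cycle 35. If 5 to 20% of the arm does so, and p = 40% over 735 + 90 = 825 days, the arm-level SAE proportion rises by 0.2 to 2.6 points. That figure includes the extra 30 days of SAE follow-up. AE discontinuations can also continue to accrue in this period, in this arm only.

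**6. Intensity of observation.** In cycles 1 and 2 there are 5 scheduled contacts with lenvatinib (C1D1, C1D8, C1D15, C2D1, C2D15) against 2 in the other arms. After screening, each arm has at least one laboratory test that is not scheduled in the others.

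**7. Scale within a biomarker group.** Arms are capped at about 25 or 40 participants (Section 10.7), so one participant is 4.0 or 2.5 points. The largest gap in the table, 6.4 points, is 1.6 or 2.6 participants; the smallest, 0.6 points, is 0.15 or 0.24.

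**The case against.** The case for leaving the plan alone is substantial. Safety is descriptive and assessed by combination within biomarker group, with no between-arm test to invalidate. Section 10.7 ties no stopping decision to an AE count, safety rests on clinical review, and exposure is already summarized. All of that is true. It makes this a matter of interpretation, but it does not make unequal windows comparable when randomized arms are set beside each other.

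A reader might infer that AE frequencies in general must differ between arms, or that the lenvatinib arm is bound to look worse. The documents do not support either reading:
- The post-treatment all-AE window is the same in every arm. The 120/90 difference changes the any-AE endpoint only when a participant's first AE is an SAE on days 91 to 120. It cannot change AE discontinuations, because treatment has already stopped.
- New anticancer therapy cuts the SAE window to 30 days everywhere, and drug-related SAEs are reportable at any time in every arm, although investigators need not actively look for them in former participants.
- A laboratory abnormality is an AE only if the investigator judges it clinically significant (Appendix 4). Scheduled testing makes AEs easier to detect in all three arms, for different tests, so no overall direction follows.
- Continuation on lenvatinib alone is open-ended, but once a participant consents to the extension study, safety events are collected under that study (Section 9.3.1).

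**Conclusion.** The point holds as a limit on interpretation. Crude SAE counts, AE and AE-discontinuation counts that include time after cycle 35, and AEs detected by single-arm tests are not directly comparable across the combinations, and Section 10.6.2 contains nothing that would make them so. The any-AE endpoint is little affected by the SAE window. The SAE artefact is roughly 0.5 to 6 points under equal, constant assumed hazards. The upper end needs short treatment, frequent SAEs and little new anticancer therapy. Added lenvatinib time after cycle 35 contributes an assumed 0.2 to 2.6 points. Within a single biomarker group these gaps usually amount to about one participant or fewer. The documents give no hazards, treatment durations or rates of new therapy, so the actual size is unknown.

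**What to change.** Keep the full-window tables and add to Section 10.6.2, or to the supplemental SAP that Section 10.1 provides for:

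- A supportive common-window table for all arms. Count AEs and AE discontinuations through the earlier of 30 days after last dose or 30 days after cycle 35. Count SAEs through the earlier of 90 days after last dose or 90 days after cycle 35, with the existing 30-day truncation at new anticancer therapy. The cycle-35 cap is needed for SAEs too, because 90 days after last dose alone would still include the lenvatinib-alone period. Define the cycle-35 date identically in every arm.
- Exposure-adjusted incidence rates, as supportive. They address unequal duration before cycle 35, which a common cut-off does not, but they assume a roughly constant hazard.
- A footnote or separate listing for laboratory-only AEs from tests scheduled in one arm: amylase/lipase (MK-4280), ACTH/cortisol (MK-1308), magnesium (lenvatinib).

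At equal treatment duration the common cut-off brings the SAE window ratio to 1.00 and the gap in step 2 to zero. All of this uses data already collected, and neither collection nor clinical management changes. The cost is a few extra tables and a second set of safety counts to explain.
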